Patients ages 18 – 65 years with a history of at least one year of migraine headache with at least 6 headache days per month, confirmed by a neurologist. All patients must meet all Preliminary Inclusion and Preliminary Exclusion criteria and will then be offered participation in the trial. Once identified, all potential participants will be consented by the Principal Investigator/Research team at Columbia University Medical Center. Subjects will then be screened with a transcranial Doppler study to determine the presence or absence of a right to left shunt. All subjects with right to left shunt, who meet subsequent laboratory criteria will proceed with the protocol until a total of 20 episodic subjects are treated with Brilinta/ticagrelor and 20 subjects with chronic headaches are treated with Brilinta/ticagrelor.

RECRUITMENT:

Subjects will be recruited from the investigators' clinic and private patient populations. Study information, which will be pre-approved by the Institutional Review Board, will be available to both referring physicians and to the subjects in printed format and on-line. Local physicians interested in referring subjects to the study will be able to set up appointments for their patients directly through the office of the Principal Investigator.

Patients will be approached for participation by the Study Investigators at the time of her/his office visit at Columbia University Medical Center or the external office of the Principal Investigator. The investigator will discuss the study with her/him in order to ascertain whether or not she/he might be interested in participation.

A member of the research team will review patient information to see if she/he meets the initial inclusion/exclusion criteria for the study. All of the information the treatment team member reviews to screen potential participants has been obtained by the clinical staff (NP's, PA's and physicians) for clinical purposes. Some examples of the type of information reviewed include the patient's age, their medication list, drug allergies, length of migraine history, migraine frequency, etc. If the patient is found to fit study criteria, the consent process begins.

INFORMED CONSENT PROCESS:

Patients who meet Preliminary criteria will be consented by a member of the treatment team. At the first screening visit, patients will sign a Screening Consent, which will give the investigators permission to perform the Transcranial Doppler Study and blood work to assure their eligibility. Once it is determined that a right to left shunt is present, the complete consent for the TRACTOR Migraine Headache Study will be completed. All questions regarding the study will be answered and the patient will have the opportunity to discuss any research related issues. No time limit will be defined and sufficient time will be given to the patient to consider participation. The patient will be given the opportunity to consult with others including family members, referring physician, etc. If she/he is interested in participating, written consent will be obtained either at that time or at any subsequent date.

SAFETY AND ADVERSE EVENTS:**Definitions of Adverse Events (see above):****Recording of Adverse Events:**

The Principal Investigator will review all adverse events and immediately be notified of any Serious Adverse Event (SAE); an electronic Adverse Event Report Form will be completed.

Adverse Event Reporting Period:

Serious Adverse Events, after assessment by the study investigator, are to be reported to all other investigators (Executive Committee) within 48 hours. The Investigator will convene the Executive Committee to review/adjudicate the event, with reporting to the IRB/FDA/AstraZeneca as required. Non-serious adverse events will be recorded in the participant study record, reviewed by the study investigator, and will be reported to the IRB/AstraZeneca as required.

Reporting of Serious Adverse Events:

The Principal Investigator is responsible for concurrently informing AstraZeneca, as well as the local authorities and ethical committees, of any serious adverse events as per local requirements. Serious adverse events that do not require expedited reporting need to be reported to AstraZeneca quarterly either as individual case reports or as line-listings.

Any SAE that is unexpected and for which there is a reasonable possibility that the drug caused the adverse event will be considered a "Suspected Unexpected Serious Adverse Reaction (SUSAR), and will be reported to the FDA in accordance with 21 CFR 312.32. This report will be submitted to the FDA as soon as possible, but no later than 15 calendar days from participant notification, and unexpected fatal or life-threatening serious adverse reactions (SARs) will be submitted no later than 7 calendar days from the initial notification. Events that are considered to be "Unanticipated Problems" or UPs, will be submitted promptly to CUMC IRB, but no later than 7 calendar days following the occurrence of the UP or first knowledge of the UP.

All Serious Adverse Event reports will be reviewed/adjudicated by the Executive Committee with reporting to the IRB/FDA as required. The Principal Investigator will be responsible for the dissemination of all serious adverse event (SAE) information to each of the study investigators.

Adverse Event Reporting forms will be used to identify and track each Adverse Event during the study. The form will capture the nature of the event (e.g. Bleeding, Shortness of Breath, etc.), the likelihood that the AE was related to the study medication, the need for treatment related to the AE, the type of treatment required, and the clinical outcome of the AE. Each AE will be classified as an anticipated or unanticipated issue with the study medication. Any bleeding AE will be further characterized (separate report form) as a major life-threatening bleed, major non-life threatening bleed or minor bleed. Additional separate report forms are available in the event of a subject mortality during the study. All AE's will be reported as safety endpoints in the final study report.

If a participant, or the female partner of a male participant should become pregnant during the study (with or without an adverse event), the pregnancy will be followed to delivery (no matter how the pregnancy ends, spontaneous abortion, elective abortion, pre or term delivery etc.) and the outcome of the pregnancy will be documented and reported as appropriate (to both FDA and to AstraZeneca). Any congenital anomaly or birth defect, in the offspring of a patient (male or female) who was taking the study drug when pregnancy occurred, will be reported to the IRB, to the FDA and to AstraZeneca as an SAE.

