Nozari et al.¹³, studied the impact of cerebral microembolization in mice, using PET scan imaging to demonstrate cortical-spreading depression (CSD), after carotid artery injections of air and particulate matter. CSD has been strongly linked to symptoms of MHA+ in humans²²⁻²⁴. Their work clearly demonstrated the potential of cerebral microembolization, from a right to left shunt, to trigger migraine without causing stroke.

A group from the Netherlands noted that there was an improvement of migraine symptoms, and a reduction in rescue medication use on warfarin,^{25,26} but there has been no further investigation of this relationship since 2004.²⁷

We formulated our study hypothesis, in part, based upon our experience with a handful of stroke patients treated with clopidogrel, due to aspirin sensitivity. Several returned reporting reduction/elimination of migraine symptoms.

As a result, 15 patients with frequent severe episodic MHA and documented RLS, were treated with a one-month trial of clopidogrel.¹⁴ None of the patients had prior stroke or TIA. All remained on baseline migraine medication throughout the month. There was a dramatic reduction or elimination of MHA symptoms in 13 of the 15 patients. Subsequently, some of the responders have been able to decrease or eliminate other migraine prophylactic agents (i.e. topiramate). Four responders have continued on clopidogrel therapy with persistent benefit, while the other 9 responders went on to have PFO closure. Of these, 8 of 9 continue to be headache-free even after discontinuation of clopidogrel. Although the preliminary results were positive, there were insufficient numbers to detect statistical significance of the results/adverse events, and a placebo effect could not be ruled out. As discussed above, headache elimination was seen in four of five patients on prasugrel who were unresponsive to clopidogrel, and proven by PRU testing to be unable to metabolize/utilize the clopidogrel.

STUDY DESIGN AND STATISTICAL PROCEDURES:

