We propose a prospective, open-label, single-arm pilot study treating 40 subjects to assess the hypothesis that P2Y12 inhibition with Brilinta/ticagrelor (90 mg PO twice a day) reduces episodic and/or chronic migraine headache symptoms in patients with right to left shunt. There will be no randomization or blinding of therapy. The study drug will be provided, free of charge, by the manufacturer, Astra-Zeneca. All subjects will be treated with the same medical regimen, and will be treated at Columbia University Medical Center or one of Principal Investigators external offices. All subjects will have an initial visit that will include the completion of a screening questionnaire (inclusion/exclusion criteria), informed consent, transcranial Doppler screening, laboratory blood testing by venipuncture (approximately 15 cc of blood = 1 tablespoon), and instruction on the use of the daily headache log (see Appendix 1, Appendix 2). Over the next 28 days, the subjects will receive an e-mail/text reminder daily with a link to complete the headache log (see below). At a second study visit, following completion of the first baseline month, the study staff will review the subject's headache log material, will release those subjects with insufficient headache days in the screening month, will assign the remaining/eligible subjects to either the episodic or chronic migraine cohort, will distribute the study drug, will administer the Brilinta/ticagrelor loading dose, and will review the medication's proper use. After 7 days of treatment with Brilinta/ticagrelor, while still on therapy, subjects will be sent for additional laboratory testing (PRU test < 10 cc of blood by venipuncture). At the completion of the 28 days (+7 days) on Brilinta/ticagrelor, each subject will have a follow-up study visit within 7 days, before discontinuing medication. At the third study visit, headache logs will be reviewed with the study staff, results will be discussed, remaining medications and empty bottles will be returned, and adverse events will be reviewed. Headache frequency while on Brilinta/ticagrelor will be compared with the documented baseline for each subject. If the Brilinta/ticagrelor therapy was effective (> 50% reduction in monthly headache days), the subject could elect to continue therapy for an additional two months, while continuing to complete daily headache logs.

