When a participant meets basic inclusion/exclusion criteria, she/he will be screened with a Power M-Mode Transcranial Doppler (TCD) examination as described by Spencer et al.²⁹ An ultrasound probe will be placed over the patient's temple and an arterial tracing will be obtained. She/he will receive a small intravenous line, through which two boluses of normal saline will be injected. Each participant will undergo initial testing in a supine position, with the head of the bed at a 30° incline, breathing normally. Secondary testing will be done with the patient in the same position, but the bolus will occur following release of a forced Valsalva, noting a reduction in cerebral blood flow velocity as an indicator of adequacy of the Valsalva strain.

All studies will be recorded electronically, and will be saved for potential review at a later time. Each participant will receive two scores, according to the Spencer Scale, one at rest and one with Valsalva. These results of the transcranial Doppler exam will be described as follows:

- *Grade 0: No embolic events.*
- *Grade 1: 1–10 cerebral embolic events.*
- *Grade 2: 11–30 cerebral embolic events.*
- *Grade 3: 31–100 cerebral embolic events.*
- *Grade 4: 101–300 cerebral embolic events.*
- *Grade 5: Greater than 300 countable discrete events.*
- *Grade 5+: Overwhelming events ("curtain" effect).*

A Spencer Grade ≥ 2 , either at rest or with Valsalva release, will be used as criteria for the presence of a right to left shunt.

Any participant without a documented right to left shunt by Transcranial Doppler will have completed her/his participation in the study and will be referred back to her/his referring physician for on-going conventional treatment of migraines.

Those participants identified with a right to left shunt will be assigned a Patient Study Number. This number will be used for maintaining participant confidentiality and as identification for entering demographic and baseline headache log information in the TRACTOR Migraine Trial Database. This number will continue with the participant throughout her/his participation in the trial, and will be used in any correspondence, Executive Committee meetings, or reports of adverse events.

Once assigned a Patient Study Number, the subject will undergo baseline laboratory screening, consisting of:

- Complete Blood Count: Hemoglobin/Hematocrit, White Blood Count
- Platelet Count

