Appendix 1:

Trial Schedule: (see attached TRACTOR Migraine Trial Flow Sheet in Appendix 2)

Study Visit #1: At the time of the first visit, study coordinator/investigators will discuss trial and subject eligibility for participation based on migraine headache frequency. The coordinator will collect all demographic information required for the study. Participant will receive explanation of the additional testing required for trial participation. After patient has been given an opportunity to ask questions, a screening consent will be signed to perform this testing. Participant will receive a Patient Study Number. Transcranial Doppler study will be performed. If negative for right to left shunt, participant will be sent back to the referring physician for on-going clinical care. If positive for right to left shunt (Spencer Grade ≥ 2) participant will be eligible to continue in the trial. The trial will be explained in detail, including participant responsibilities, and the patient will receive written study materials. A complete TRACTOR Migraine Headache Trial consent will be signed. The participant will receive a test e-mail/text message and must demonstrate the ability to answer the headache log questions. A Quality of Life Survey will be taken. Laboratory screening is done. End of visit.

Study Phase 1:
(28 Days) Within 72 hours of the laboratory evaluation, participant will be notified of results of laboratory testing and ability to continue participation. She/he will begin to receive daily reminders (e-mail/text message) to log-in to answer the headache log questions. A follow-up appointment will be scheduled within 7 days of the completion of 28 days of headache monitoring.

Study Day 29: Headache log entries will be reviewed by the Study Coordinator to determine final eligibility for trial based on the number of headache days documented.

Study Visit #2: Must occur within seven days of completion of baseline headache log. Participant will return to receive her/his medication. She/he will receive a loading dose of 180 mg of Brilinta/ticagrelor and an additional 70 tablets and will again review the responsibilities for participation with the coordinator. The participant will be observed for 30 minutes after taking the first medication dose.

Study Phase 2:

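### No minimum interval separates the bolus Doppler at Visit 1 from the first counted baseline day, so a provoked attack could inflate the baseline alone (minor)

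*Combined protocol and SAP*

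**What the plan says.** **The screening test.** Under Transcranial Doppler Screening, each participant is tested at rest and after a Valsalva: "She/he will receive a small intravenous line, through which two boluses of normal saline will be injected". A shunt is declared present at Spencer Grade 2 or more, and Grade 2 is defined as "11–30 cerebral embolic events". Everyone who continues has therefore had at least 11 counted events in at least one of the two conditions. The flow chart in Appendix 2 marks the Doppler at Study Visit #1 only.

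**The premise.** The Background summarises a mouse study of cerebral microembolization and concludes: "Their work clearly demonstrated the potential of cerebral microembolization, from a right to left shunt, to trigger migraine without causing stroke".

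**The start of the log.** The Study Design section lists the Doppler among the procedures of the initial visit and continues: "Over the next 28 days, the subjects will receive an e-mail/text reminder daily with a link to complete the headache log". Appendix 1 (Study Phase 1) says "Within 72 hours of the laboratory evaluation, participant will be notified of results of laboratory testing and ability to continue participation", and describes the daily reminders next. Appendix 2 places Phase 1 after all screening is complete. None of these states a minimum gap, and the description of the Baseline-Monitoring Phase does not drop any early days.

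**The uses of the log.** The 28-day count decides whether a subject continues (at least 6 headache days). It is also the subject's own baseline for the primary efficacy endpoint, a fall of 50% or more in monthly headache days. On design, the protocol says "There will be no randomization or blinding of therapy".

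**The concern.** The exposure is one-sided. A procedure that sends countable emboli to the brain comes before the baseline month and not before the treatment month, and only subjects in whom it did so are carried forward. If the Background premise applies to this procedure even in part, some subjects could have an attack in the first logged days that they would not otherwise have had.

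The documents' own definitions allow such an attack to be counted. An attack lasts 4 to 72 hours, the daily log asks about the previous 24 hours, and headaches longer than 24 or 48 hours count as two or three days.

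Extra baseline days act in one direction on the endpoint: they make a 50% fall easier to reach and the 6-day entry rule easier to pass. There is no concurrent arm in which the same artefact would appear and cancel. The protocol intends to use the observed response rate to size the later randomized trial, so an upward bias would carry forward even though the pilot is descriptive.

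**Working it through.** The plan states no figure for Doppler-related headache, so there is nothing of its own to reproduce. The check asks how much the responder rate would move if some early logged days were provoked.

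**Inputs from the documents:** 28-day baseline, entry at 6 or more logged days, Responder if the fall is 50% or more.

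**Assumptions:**
- Days are independent.
- True headache days per 28 are *m* = 8 (episodic) or 20 (chronic).
- The true drug reduction is *r* = 0 or 0.4.
- In an affected subject the first *k* = 1, 2 or 3 logged days are headache days.
- The treatment window is 28 days.

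**Model:**
- Logged baseline B = k + Binomial(28 − k, m/28).
- Treatment count T ~ Binomial(28, m(1 − r)/28).
- Responder probability = P(T ≤ B/2, given B ≥ 6).

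| True days, reduction | k = 0 | k = 1 | k = 2 | k = 3 |
|---|---|---|---|---|
| 8, none | 9.0% | 10.7% | 13.0% | 15.8% |
| 8, 40% | 47.2% | 51.1% | 55.7% | 60.8% |
| 20, 40% | 27.4% | 29.1% | 30.8% | 32.5% |

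At 20 days with no drug effect the probability is close to zero whatever *k* is.

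**Why the chronic cohort moves little.** A provoked day adds to the count only if it would otherwise have been free of headache, so the expected net gain is k(1 − m/28). For k = 3 this is 3 × 20/28 = 2.14 days at m = 8, but 3 × 8/28 = 0.86 days at m = 20.

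**Overdispersion.** With beta-binomial counts (rho = 0.05, also an assumption) the shifts shrink. At 8 days and 40% reduction the probability goes from 56.8% to 58.2%, 59.9% and 62.0%. At 20 days and 40% it goes from 35.7% to 36.8%, 38.0% and 39.2%.

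**Entry.** For a subject whose true mean is 5 days, the chance of logging 6 or more rises from 38% to 54% with k = 1.

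**Whole-trial shift.** The affected share is not in the documents, so 10% to 30% is assumed. The shift is the share times the rise in affected subjects. The smallest rise in the table is 29.1 − 27.4 = 1.7 points, and 0.10 × 1.7 ≈ 0.2 points. The largest is 60.8 − 47.2 = 13.6 points, and 0.30 × 13.6 ≈ 4 points. In a cohort of 20, a 4-point shift is 0.04 × 20 = 0.8 of a subject.

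**The case against.** The strongest reply is that the mechanism is inferred. No section says the Doppler provokes headache. The cited animal finding came "after carotid artery injections of air and particulate matter" in mice, whereas the screening test is an intravenous injection described only as normal saline. The protocol's leading theory centres on activated platelets, through micro-clots or vasoactive substances. This stands. A reader might infer that the Doppler does cause migraine and that the baseline is inflated, but the documents support only the possibility.

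Second, a reader of the Study Design section might infer that logging starts immediately after the Doppler. The eligibility text and both appendices place it after laboratory clearance, with results due within 72 hours, so an attack could fall partly or wholly before the first logged day. This also stands, and it makes k = 3 an extreme case. But 72 hours is an upper limit: same-day clearance would leave no gap.

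Third, a reader might add the provoked days on top of an ordinary 28-day count. At 20 days and a 40% reduction that gives 34%, 40% and 47% for one to three extra days, against 29%, 31% and 32% (32.5% before rounding) when the attack simply occupies the first logged days. The larger figures ignore the days that would have been headache days anyway.

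Two smaller replies have some force. A history of at least 6 headache days per month is required separately, which limits wrongful entry. A treatment count over 28 to 35 days, if not scaled, would push the response rate down. Neither removes a bias that enters through the baseline.

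**Conclusion.** The gap in the protocol is real and its consequence is minor. No minimum interval is set between the Doppler and the first counted baseline day. On the protocol's own premise a provoked attack could add baseline days that have no counterpart in the treatment month, and any such days favour a Responder label. Whether this happens, and how often, cannot be settled from the documents.

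Under the stated assumptions one provoked day raises an affected subject's responder probability by about 2 to 4 points in the settings tabulated. The effect in the chronic cohort is small, and the overall shift is about 0.2 to 4 points if 10% to 30% are affected. In a descriptive pilot of 40 subjects with no success threshold, this would not by itself overturn a conclusion. The point is worth acting on because the direction is predictable and the remedy is nearly free.

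**What to change.** In the Study Design section, the Baseline-Monitoring Phase description and Appendix 1 (Study Phase 1), make one of two changes:

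- Set the first counted baseline day at least 4 full days after the Doppler. This covers the 72-hour attack limit plus the 24-hour look-back of the log.
- Alternatively, log 32 days and count only days 5 to 32, both for the 6-day entry rule and for the response denominator.

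Under the second option, tabulate the headache rate on days 1 to 4 against days 5 to 32. That would show whether provocation occurs at all, which is useful for the planned randomized trial.

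At a minimum, pre-specify a sensitivity analysis of the responder rate that omits the first 4 days after the Doppler, with the remaining baseline scaled to a 28-day rate. This repairs the denominator but cannot undo entry decisions already made.

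The cost is one sentence in each of three places and up to 4 more days before Visit 2. No extra visit, test or staff is needed.
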